4.3 PROJECTED RECRUITMENT TIME

Based on the available population and expected consent rate, we anticipate it will take approximately six months to recruit mothers for each cohort. Patients will have MRIs performed in the third trimester (28 weeks to 40 months), and infant data will be collected after completion of pregnancy.

Table. Study timeline, * means completed

Career Development Plans	Y1	Y2	Y3
-IRB approval for prospective study	X		
-Complete retrospective data analysis	X		
-Meet with OB groups for patient recruitment	*		
-Prospective study fetal MRI data collection		X	X
-Complete data collection, prepare manuscript, and submit abstracts		X	X

4.4 STATISTICAL ANALYSIS PLAN

Comparisons will be considered statistically significant at the $p<0.05$ level. No adjustments for multiple comparisons will be made considering the exploratory nature of this study. The effect sizes measured in this exploratory grant will be used as the basis for power calculations for future grant applications.

Data will be reported in terms of medians and interquartile ranges and frequencies. Ultrasound growth parameters and birth growth parameter z-scores will be calculated per fetal growth, WHO, and Fenton growth charts, respectively. Generalized linear models for repeated measures will be used to compare weight and length z-scores to each type of adipose volume and PDFF measurement. Generalized linear models for repeated measures will be used to compare maternal BMI prior to pregnancy to adipose tissue volumes and PDFFs. Generalized linear models for repeated measures will be used to compare ultrasound growth parameters to adipose tissue volumes and PDFFs. ANOVA analyses will compare visceral, subcutaneous, and brown adipose tissue volumes, and hepatic PDFF across different groups (gestational diabetes, IUGR and healthy infants).

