1.2 HYPOTHESES AND SPECIFIC AIMS

To accomplish our objectives, our aims and hypotheses are as follows:

Specific Aim 1:

In a prospective study in women with healthy pregnancies and women with fetuses that have intrauterine growth restriction (IUGR) and gestational diabetes, we will quantify fetal subcutaneous, visceral, and brown adipose tissue volumes and proton-density fat fraction (PDFF) using FB-MRI in the third trimester.

Hypothesis 1: Using a FB-MRI technique we will find the following,

- 1) The growth restricted fetus will have less visceral, subcutaneous, and brown adipose tissue volume and PDFF when compared to healthy fetuses and fetuses whose mothers have gestational diabetes.
- 2) Fetuses whose mothers have gestational diabetes will have a greater subcutaneous and visceral adipose tissue volume and PDFF compared to healthy fetuses.

Specific Aim 2:

In a prospective study in pregnant women and their fetuses, we will compare volume and PDFF measurements of fetal visceral, subcutaneous, and brown adipose tissue obtained with FB-MRI to birth growth parameters of these infants.

Hypothesis 2: The volume and PDFF of fetal visceral and subcutaneous adipose tissue will correlate positively with birth weight and length z-score.

1.3a. BACKGROUND:

Pediatric obesity is a public health crisis with increasing prevalence worldwide. 19% of children and adolescents in the United States are obese¹. Pediatric obesity is associated with an increased risk for adult onset metabolic syndrome, which refers to the co-occurrence of obesity, insulin resistance, dyslipidemia, hypertension, and non-alcoholic fatty liver disease². There is also a tremendous amount of evidence suggesting that obesity and the metabolic syndrome have fetal origins due to abnormal fetal growth and maternal conditions³⁻⁶.

Impaired fetal growth is a major cause of perinatal morbidity and mortality. Infants with intrauterine growth restriction (IUGR) and infants who are born small for gestational age (SGA) and large for gestational age (LGA) have an increased risk for future obesity, insulin resistance, cardiovascular disease, and associated metabolic complications. IUGR infants have been found to have insulin resistance due to epigenetic changes in the liver and reduced pancreatic beta cell mass³. IUGR infants also exhibit satiety dysregulation secondary to impaired leptin and ghrelin⁴.

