It is important to be mindful that body composition can be measured using different technologies: dual-energy X-ray absorptiometry (DXA), computed tomography (CT), ultrasound, air displacement plethysmography (ADP, commercially known as the PeaPod), and magnetic resonance imaging (MRI). DXA and ADP cannot be used in a fetal model due to poor image quality. DXA is able to estimate the amount of subcutaneous and visceral adipose tissue within the android region, and correlates well with

CT¹². However, DXA and CT both require radiation, which is undesirable for the fetus and child. While ultrasound does not involve radiation, is an inexpensive imaging tool, and can be used in the utero and extra-utero environment, ultrasound is dependent on the skill of the sonographer and results can be variable. In contrast, MRI is a noninvasive imaging tool that does not involve ionizing radiation and can be used to accurately and longitudinally quantify the volume of adipose tissue. MRI can also measure the proton-density fat fraction (PDFF) in percent, which is used as a biomarker for tissue fat content.

Fetal MRI is becoming increasingly utilized as an adjunct to ultrasound for maternal or fetal conditions related to pregnancy. The American College of Obstetricians and Gynecologists released a statement in 2017 stating that MRI is not dangerous and should be used prudently to answer a clinical question. Today, MRI is commonly utilized in cases of placenta accreta¹³ and fetal anomalies such as congenital diaphragmatic hernia, congenital heart disease, and neurological anomalies. There are difficulties with fetal MRI due to lack of control of fetal movement. Our group has developed a free-breathing (FB) MRI technique and has utilized this technology in adults, pregnant women, adolescents, and infants¹⁴⁻¹⁸.

To date, there has been little research pertaining to fetal body composition using MRI. Previously, using T1-weighted MR images, it has been difficult to detect adipose tissue in the second trimester^{19,20}. Blondiaux et al (2018) looked at subcutaneous adipose tissue in T1-weighted images starting in the second trimester and found the signal was isointense at 26 weeks and all areas were hyperintense by 33 weeks in a progressive fashion from the nuchal region, buttocks, thigh and back²¹. However, now using 3T MRI for fetal imaging, subcutaneous adipose tissue is more easily identified in the mid and late second trimester²².

1.3b. PRELIMINARY DATA:

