2.1 STUDY DESIGN

This is a prospective pilot study that will be used to generate data to provide a power analysis for a larger, longitudinal study that will follow fetuses at risk for obesity.

2.2 PRIMARY OUTCOMES:

The primary outcome will be visceral adipose tissue volume and PDFF for the three patient populations: mothers with growth restricted fetuses, mothers with gestational diabetes, and mothers with healthy pregnancies.

2.3 SECONDARY OUTCOMES:

The secondary outcomes will be subcutaneous and brown adipose tissue volume and PDFF, as well as hepatic PDFF, for the three patient populations listed above. Another secondary outcome will be growth parameters of the neonates.

2.4 POTENTIAL RISKS AND BENEFITS:

Subjects may receive no benefit from participating in this study. However, information from this study may improve the understanding of childhood obesity, inform management strategies, and may help prognosticate which infants are at higher risk for obesity.

The research MRI scans required for this study do not require sedation, involve ionizing radiation, or require any contrast administration. MRI scans are a painless test. In other words, the FB-MRI performed for research purposes will NOT require contrast or sedation. However, patients/subjects can experience claustrophobia inside the MRI scanner. Patients with a history of claustrophobia will be excluded from this study. Noise from the scanner during an MRI scan will be mitigated by providing earplugs and headsets to the patients/subjects. Lastly, because MRI scans use magnetic fields, subjects with any metal (e.g., internal metal clips or implants) will be excluded from the study. All subjects will be asked to remove any metal (i.e. earrings, metal belts, etc).

Because information will be collected from each subjects' medical record, there is the possibility of a breach of confidentiality. However, all precautionary measures will be taken to ensure that confidentiality and privacy is maintained, and that data is stored securely. All conversations with subjects and their families will occur in a private setting.

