3.1 STUDY POPULATION

In this study, anticipating a 10-15% dropout rate, we plan to recruit 18 mothers: 6 healthy pregnant women, 6 women with IUGR fetuses, and 5 mothers with gestational diabetes.

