4.1 SAMPLE SIZES AND POWER ESTIMATES

This study will not be powered considered that this is a pilot study. Previous studies by our group in infants/children have used a sample size of 10 to 20 subjects, and these sample sizes were feasible and adequate to develop a new protocol

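### Section 4.4 bases the next study's power calculation on this pilot's measured effect sizes but plans no interval or other allowance for their imprecision at about 5 completers per cohort

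*Combined protocol and SAP*

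**What the plan says.** Section 2.1 (Study design) says the pilot "will be used to generate data to provide a power analysis for a larger, longitudinal study". Section 4.4 (Statistical analysis plan) names the input to that calculation: "The effect sizes measured in this exploratory grant will be used as the basis for power calculations for future grant applications".

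On size, section 3.1 allows for 10-15% dropout and states: "we plan to recruit 18 mothers: 6 healthy pregnant women, 6 women with IUGR fetuses, and 5 mothers with gestational diabetes". Section 4.1 adds: "This study will not be powered considered that this is a pilot study". It justifies the size by feasibility and by the group's earlier studies.

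On output, section 4.4 says: "Data will be reported in terms of medians and interquartile ranges and frequencies". It adds ANOVA across the cohorts, generalized linear models for the associations, and a 0.05 significance level without multiplicity adjustment. No confidence interval, standard error, conservative limit or sensitivity range for an effect size or SD appears anywhere in the document.

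Two kinds of effect could feed the next study: the differences between cohorts (Aim 1) and the associations with birth size (Aim 2). Hypothesis 2 in section 1.2 reads: "The volume and PDFF of fetal visceral and subcutaneous adipose tissue will correlate positively with birth weight and length z-score".

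**The concern.** The planning value is the declared product of this pilot. Calling the study unpowered and exploratory explains why it has no power calculation of its own and no multiplicity adjustment. It does not say how a value measured in about 5 women per cohort should be carried into the next design.

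An interquartile range describes spread between subjects. It is not an interval for a difference between cohorts or for a correlation. If the measured effect size is used as it stands, the next study could be much too small or much too large, and none of the planned summaries states that uncertainty directly. The cost would fall on the next study's design and funding.

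**Working it through.** The plan has no power-based figure to reproduce. Effect size, SD, target power and sidedness are not given, so those below are assumptions, shown over a range.

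**1. Completers (section 3.1).** The listed cohorts sum to 6 + 6 + 5 = 17, against the stated 18. The mismatch needs reconciling but does not alter the point.
- Cohort of 6: 6 × 0.85 = 5.1 to 6 × 0.90 = 5.4.
- Cohort of 5: 5 × 0.85 = 4.25 to 5 × 0.90 = 4.5.
- All mothers: 17 gives 14.5 to 15.3; 18 gives 15.3 to 16.2.

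**2. Difference between two cohorts.** With m = √(n1·n2/(n1+n2)), t = d × m follows a non-central t distribution on n1+n2-2 df. At 5 v 5, m = √(25/10) = 1.581. An assumed observed d of 0.8 gives t = 1.265 on 8 df. The 95% limits for the non-centrality are -0.823 and 3.282; divided by 1.581 they give **-0.52 to 2.08**. At 5 v 4 the interval is -0.60 to 2.15, and with no dropout (6 v 6) it is -0.40 to 1.97.

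In the normal approximation, n per group = 2 × (1.960 + 0.842)²/d² = 15.7/d². At d = 0.8 this is 24.5, so 25. At the upper limit, 15.7/2.08² = 3.6, so 4. The lower limit is below zero, so no finite n follows.

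**3. Association (Aim 2).** Fisher z for r = 0.5 is 0.549. With n = 15 the half-width is 1.96/√12 = 0.566, so z runs from -0.016 to 1.115 and r from **-0.02 to 0.81**. At n = 14 it is -0.04 to 0.82; at n = 16, 0.01 to 0.80.

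**4. Sizing on the point estimate alone.** Assume a two-group comparison stands in for the next study, with 80% power, two-sided 0.05, exact t power and a pilot of 5 v 5. Worked case, true d = 0.8: 26 per group are needed. A planned n of at most 13 arises when observed d is at least 1.145, with probability 0.328. A planned n of at least 52, or a wrong sign, arises when observed d is below 0.560, with probability 0.346. The remainder is 1 - 0.328 - 0.346 = 0.326 (0.327 before rounding).

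| True d | n needed per group | At most half | Within a factor of two | At least double, or wrong sign | Wrong sign alone |
|---|---|---|---|---|---|
| 0.5 | 64 | 39% | 21% | 40% | 21% |
| 0.8 | 26 | 33% | 33% | 35% | 10% |
| 1.0 | 17 | 27% | 42% | 31% | 6% |
| 1.5 | 9 | 17% | 61% | 21% | 1% |
| 2.0 | 6 | 16% | 71% | 13% | 0% |

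For correlations, a simulation of 400,000 pilots with n = 15 puts the planned n within a factor of two in 32%, 55% and 84% at true r of 0.3, 0.5 and 0.7 (85, 30 and 14 needed).

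**5. The SD.** Pooled over three cohorts of 5, df = 15 - 3 = 12. The 95% limits are √(12/23.34) = 0.72 and √(12/4.404) = 1.65 times the estimate. One more df spent on gestational age (11 df) makes them 0.71 and 1.70.

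**6. Other planning rules, same model.** Percentages are pilots with planned n within a factor of two of the n needed at the true effect, for true d 0.5/0.8/1.0/1.5/2.0.

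| Rule | Within a factor of two |
|---|---|
| Observed d alone | 21/33/42/61/71 |
| Pre-set difference equal to the truth, pilot SD | 90/91/93/96/95 |
| Pre-set difference 1.25 times the truth, pilot SD | 68/69/76/83/79 |
| Pre-set difference 1.41 times the truth, pilot SD | 46/47/57/66/61 |
| Pre-set difference 0.8 times the truth, 80% upper limit for the SD | 38/40/40/51/61 |

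At 1.25 times the truth, 88-90% of the planned studies are too small, against about 51-52% with observed d alone, although severe undersizing is less common at true d of 0.5 to 1.0.

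**7. Gestational age.** Section 4.3 says: "Patients will have MRIs performed in the third trimester", starting at 28 weeks. Section 1.3a (Background) cites a study in which "the signal was isointense at 26 weeks and all areas were hyperintense by 33 weeks in a progressive fashion". Gestational age at imaging is collected (section 3.2.3), but section 4.4 does not adjust for it. If it explained an assumed 25-50% of within-cohort variance, the unadjusted SD would be 1/√0.75 = 1.15 to 1/√0.50 = 1.41 times the adjusted SD, and n would be 1.33 to 2.0 times as large.

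**The case against.** The strongest reply is that section 4.4 makes effect sizes a basis for later calculations without saying that a point estimate will be inserted unadjusted. That stands. A reader might infer such a commitment, but the text leaves the use open, so the percentages in step 4 are conditional on that use. The wrong-sign pilots also deserve discounting, because no team would turn one into a sample size. Without them, the share planned at least double is about 19/24/26/20/13%.

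A reader might also infer that the report would hide the imprecision. It would not: cohort sizes, interquartile ranges and p-values would be visible, and an approximate interval could be worked out. What is missing is a planned statement of it.

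The two-group comparison is a stand-in, since section 2.1 describes the next study only as larger and longitudinal, and the results depend on the assumed true d.

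A third tempting inference is that section 4.4 must require a pre-set important difference with an upper limit for the SD. Step 6 does not support that. The documents give no such difference. One set too low with the upper SD limit does worse than the observed d when true d is 1.5 or 2.0 and slightly worse at 1.0. One set too high mostly undersizes. It is a trade-off, so an option only.

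The gestational-age evidence in section 1.3a concerns subcutaneous signal on T1-weighted images, not visceral volume or PDFF, so it motivates showing both SDs and proves nothing about the primary outcome.

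Finally, intervals could be computed later from the same data. True, but the rule for using the estimates is already written and is silent on their uncertainty.

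**Conclusion.** The point holds in this form: the plan names its effect sizes as the planning input and provides neither an interval nor an allowance for their imprecision. The width of the intervals in steps 2 and 3 needs only normality and the completer numbers derived from section 3.1. It changes little between 5 v 4 and 6 v 6, so neither the dropout range nor the 17-against-18 mismatch matters. The risk of misplanning needs more: use of the point estimate alone, a two-group design, 80% power, two-sided 0.05 and the listed true effects. Under those assumptions it is large for small and moderate effects and still present at 2.0 SD, where 29% of pilots miss by a factor of two or more.

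The lack of power in this pilot is declared in section 4.1 and is not the defect.

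**What to change.** In section 4.4, for each outcome meant to inform the next study:
- Report cohort means, the pooled SD and pairwise mean differences with 95% CIs (log scale if skewed), beside the medians and interquartile ranges. Include visceral PDFF, which is primary in section 2.2 but absent from the ANOVA list in section 4.4.
- Report the Aim 2 correlations with 95% CIs.
- Give the SD both unadjusted and adjusted for gestational age at scan.

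Amend the effect-size sentence along these lines: *Future power calculations will not rest on the observed point estimate alone. They will show the required sample size across the confidence interval for the effect and the SD, or will use a separately justified important difference with the pilot SD and its uncertainty.*

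The cost is a few more summary columns, one degree of freedom for the gestational-age adjustment, and a wider or less favourable range of future sample sizes to present to funders. If the second route is chosen, the team must justify the difference. No extra participants or scans are needed.

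### Visceral PDFF is one of two primary measures, but the only between-cohort analysis in section 4.4 leaves it out

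*Combined protocol and SAP*

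**What the plan says.** **Outcomes.** Section 2.2 states: "The primary outcome will be visceral adipose tissue volume and PDFF for the three patient populations". Section 2.3 continues: "The secondary outcomes will be subcutaneous and brown adipose tissue volume and PDFF, as well as hepatic PDFF", for the same three populations. Hepatic, subcutaneous and brown PDFF are all listed as secondary, so the PDFF in section 2.2 can only be visceral.

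**Hypotheses.** Hypothesis 1 in section 1.2 is about differences between cohorts and names PDFF each time. Its first part reads "The growth restricted fetus will have less visceral, subcutaneous, and brown adipose tissue volume and PDFF when compared to healthy fetuses", and it makes the same prediction against the gestational diabetes cohort. Its second part says that fetuses of mothers with gestational diabetes "will have a greater subcutaneous and visceral adipose tissue volume and PDFF compared to healthy fetuses".

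**Analyses.** Section 4.4 has three sentences on generalized linear models. They "compare weight and length z-scores to each type of adipose volume and PDFF measurement", "compare maternal BMI prior to pregnancy to adipose tissue volumes and PDFFs" and "compare ultrasound growth parameters to adipose tissue volumes and PDFFs". One sentence then compares cohorts: "ANOVA analyses will compare visceral, subcutaneous, and brown adipose tissue volumes, and hepatic PDFF across different groups", the groups being gestational diabetes, IUGR and healthy. Section 4.4 also sets a 0.05 significance level, declines multiplicity adjustment, plans medians and interquartile ranges, and says the effect sizes will be used to power later studies.

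**The concern.** The outcome sections and the analysis section do not match. If section 4.4 is followed literally, Hypothesis 1 is never tested for PDFF in any adipose depot, and one of the two primary measures gets no cohort comparison. If the team compares visceral PDFF anyway, it does so outside the plan, with nothing fixed in advance for a primary measure. Section 2.1 gives the study's purpose as supplying data for the power analysis of a larger study, and for visceral PDFF the plan names no cohort effect to estimate.

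A secondary point follows from the same sentence. Hypothesis 1 is pairwise and directional, whereas a three-group ANOVA gives an overall test. Section 4.4 specifies no pairwise difference and no interval. Medians and interquartile ranges, if reported by cohort, would show direction and rough size but not the precision of a difference.

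**Working it through.** The plan gives no effect size, standard deviation or power for this comparison, so there is no figure to reproduce. The main check matches each outcome to an analysis.

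**1. Fat measures defined by cohort against the cohort ANOVA**

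| Measure | Status (2.2, 2.3) | In Hypothesis 1 | In cohort ANOVA (4.4) |
|---|---|---|---|
| Visceral volume | Primary | Yes | Yes |
| Visceral PDFF | Primary | Yes | **No** |
| Subcutaneous volume | Secondary | Yes | Yes |
| Subcutaneous PDFF | Secondary | Yes | **No** |
| Brown volume | Secondary | Yes | Yes |
| Brown PDFF | Secondary | Yes | **No** |
| Hepatic PDFF | Secondary | No | Yes |

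There are 3 depots × 2 measures + 1 hepatic measure = 7. The ANOVA lists 4, so 7 − 4 = 3 are missing. Of the two primary measures, one is covered.

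**2. Could the ANOVA sentence be read to include depot PDFF?** Not naturally. The word for volumes closes the list of depots, and the only PDFF in the sentence is qualified as hepatic. All three model sentences in the same paragraph name volume and PDFF together, so the authors wrote both where both were meant.

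**3. Do the generalized linear models supply the comparison?** No. They relate the fat measures to birth z-scores, pre-pregnancy BMI and ultrasound parameters. None names cohort as a factor. The z-score model serves Hypothesis 2.

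**4. Share of Hypothesis 1 affected.** Expanding its two parts into pairwise claims:
- IUGR against healthy and against gestational diabetes: 2 pairs × 3 depots × 2 measures = 12
- Gestational diabetes against healthy: 1 pair × 2 depots × 2 measures = 4

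The total is 16. Half, 8, concern PDFF and have no cohort analysis.

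**5. Secondary point: precision of a pairwise difference.** In units of the pooled within-cohort SD, assuming equal variances, the 95% interval half-width is t(0.975, df) × √(1/n₁ + 1/n₂). Section 3.1 lists 6 healthy, 6 IUGR and 5 gestational diabetes, which sum to 17 although the stated total is 18. The list is used here.
- 6/6/5, df = 17 − 3 = 14, t = 2.145. IUGR–healthy: 2.145 × √(1/6 + 1/6) = 1.24 SD. Either pair with gestational diabetes: 2.145 × √(1/6 + 1/5) = 1.30 SD.
- 5/5/5, df = 15 − 3 = 12, t = 2.179. Every pair: 2.179 × √(2/5) = 1.38 SD.

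The second case assumes one loss in each of the two larger cohorts: 2/17 = 11.8%, within the 10–15% dropout that section 3.1 anticipates.

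**The case against.** The strongest reply is that little rests on this test. Sections 2.1, 4.1 and 4.4 describe an unpowered, exploratory pilot without multiplicity control. Aim 1 is to quantify fat, and section 2.2 names measurements without naming a test. PDFF will be measured, and medians and interquartile ranges are planned. ANOVA is the only between-group method in section 4.4 and is already applied to hepatic PDFF, a measure of the same kind, so extending it to the depots is the obvious intent.

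Part of this stands. No confirmatory claim depends on a visceral PDFF p-value, and a self-serving choice of test is possible rather than shown. The gap remains, however. Hypothesis 1 predicts cohort differences in PDFF, section 4.4 sets a significance level for comparisons, and the descriptive summaries are neither comparisons nor stated to be by cohort. Pilot status excuses low precision. It does not explain testing a secondary PDFF and omitting the primary one.

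It is also fair to say that asking for pairwise intervals is good practice rather than the repair of a contradiction, and that the half-widths say nothing about the PDFF omission. They are kept separate here for that reason. A further limit applies to any cohort comparison, including the one proposed. Scans are spread over the third trimester (section 4.3), and section 1.3a describes fat signal developing progressively with gestation. Gestational age at imaging is collected (section 3.2.3 B) but is not in the ANOVA, so unadjusted differences could partly reflect scan timing.

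**Conclusion.** The concern holds and should be corrected. As written, section 4.4 gives no cohort comparison for 1 of 2 primary measures or for 3 of 7 fat measures, and 8 of the 16 pairwise claims in Hypothesis 1 go without an analysis. These counts describe one omission and rest only on the plain reading of sections 1.2, 2.2, 2.3 and 4.4. A drafting slip is the likeliest cause, which makes it easy to repair but does not remove the mismatch.

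The lack of pairwise estimates is a lesser point and carries none of the weight of this conclusion. Its half-widths of 1.24 to 1.38 SD assume equal variances and the cohort sizes shown. They indicate that point estimates alone would be a weak basis for powering a later study.

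**What to change.** **Required.** In section 4.4, extend the cohort ANOVA to visceral, subcutaneous and brown PDFF, so that the sentence covers volume and PDFF for every depot, as the three model sentences do, as well as hepatic PDFF. Coverage rises from 4 to 7 of 7 fat measures and from 1 to 2 of 2 primary measures.

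**Lower priority.** For both volume and PDFF, report pairwise differences with 95% confidence intervals: IUGR–healthy and IUGR–gestational diabetes for all three depots, and gestational diabetes–healthy for visceral and subcutaneous fat. Later power calculations should use these intervals as well as the point estimates.

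**Cost.** One clause and a few more model runs. Section 3.2.3 C already provides for PDFF measurement from the maps, so data collection does not change. The downside is three more unadjusted ANOVA tests, or 3 × 0.05 = 0.15 further false positives expected if there were no cohort differences in those three measures, together with wide pairwise intervals. Section 4.4 already accepts unadjusted exploratory testing.

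### Hypothesis 1 predicts direction cohort by cohort, but the only cohort test named is a three-group ANOVA, and a significant omnibus F establishes neither numbered part

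*Combined protocol and SAP*

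**What the plan says.** Section 1.2 numbers two predictions. Part 1 reads "The growth restricted fetus will have less visceral, subcutaneous, and brown adipose tissue volume and PDFF when compared to healthy fetuses", and continues to the diabetes cohort as a second comparator. Part 2 reads "Fetuses whose mothers have gestational diabetes will have a greater subcutaneous and visceral adipose tissue volume and PDFF compared to healthy fetuses". Both are statements about named pairs of cohorts, and both have a sign.

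Section 4.4 gives one sentence on cohort comparisons: "ANOVA analyses will compare visceral, subcutaneous, and brown adipose tissue volumes, and hepatic PDFF across different groups (gestational diabetes, IUGR and healthy infants". It names no pairwise difference, contrast, ordered test or sidedness. The other models in that section relate the fat measures to birth z-scores, maternal BMI and ultrasound growth, not to cohort. Two further sentences bear on the point: "Comparisons will be considered statistically significant at the $p<0.05$ level" and "No adjustments for multiple comparisons will be made considering the exploratory nature of this study". Section 4.4 also says that the effect sizes found here will be the basis of later power calculations, and section 4.1 says that the study is not powered.

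Read literally, the ANOVA sentence covers the three adipose volumes and hepatic PDFF. Hypothesis 1 covers both volume and PDFF of each depot.

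**The concern.** A test should answer the question that the hypothesis asks. The F test on 2 numerator degrees of freedom asks whether the three means are all equal. It gives the same answer if the predicted order is reversed, and it can be significant because of one cohort alone. A reader who follows section 4.4 as written could report a significant ANOVA as support for Hypothesis 1 when one part is false, or when the differences run the wrong way.

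The pilot's product is also at stake. Its stated purpose is to supply effect sizes for a larger study. The quantities that correspond to Hypothesis 1 are differences between named cohorts with their uncertainty, and section 4.4 does not commit to reporting them. It promises medians, interquartile ranges and frequencies.

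**Working it through.** The plan contains no power or effect-size calculation, so there is no figure of its own to reproduce.

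**Step 1: match each prediction to a comparison.**

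| Prediction | Measures | Comparison needed | Named in 4.4? |
|---|---|---|---|
| Part 1 | visceral, subcutaneous, brown | IUGR minus healthy | no |
| Part 1 | visceral, subcutaneous, brown | IUGR minus diabetes | no |
| Part 2 | visceral, subcutaneous | diabetes minus healthy | no |

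**Step 2: inputs.** Section 3.1 lists "6 healthy pregnant women, 6 women with IUGR fetuses, and 5 mothers with gestational diabetes", which sums to 17, and also says "anticipating a 10-15% dropout rate, we plan to recruit 18 mothers". Applying the dropout range to 17 gives 17 × 0.90 = 15.3 and 17 × 0.85 = 14.5 completers, so I use 5/5/5 for completers and 6/6/5 for the listed cohorts. Alpha is 0.05 (section 4.4), taken as two-sided for contrasts because sidedness is not stated. The documents give no SD or effect size. I assume normal data with a common SD of 1 and show several mean patterns, always in the order IUGR / healthy / diabetes.

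**Step 3: omnibus F.** With grand mean m, the noncentrality is λ = Σ n(μ − m)². Power is the probability that a noncentral F on (2, N − 3) df exceeds its 5% critical value.

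For −2/0/0 at 5/5/5, m = −0.667 and λ = 5 × (1.333² + 0.667² + 0.667²) = 13.33. The critical value of F(2, 12) is 3.885, and power is 82.6%.

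| Cohort sizes | Means (SD) | Truth | λ | F significant |
|---|---|---|---|---|
| 5/5/5 | −2/0/0 | part 2 false | 13.33 | 82.6% |
| 5/5/5 | −1/0/+1 | as predicted | 10.00 | 70.2% |
| 5/5/5 | +1/0/−1 | order fully reversed | 10.00 | 70.2% |
| 6/6/5 | −1.5/0/0 | part 2 false | 8.74 | 66% |
| 6/6/5 | −1.5/0/−0.5 | diabetes below healthy | 6.97 | 55% |

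The second and third rows are identical because λ depends only on squared deviations.

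**Step 4: named differences.** For cohorts a and b, δ = (μa − μb) / √(1/na + 1/nb), referred to a noncentral t on N − 3 df with pooled variance. Under −1/0/+1:

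| Difference | δ at 6/6/5 | Power at 6/6/5 | Power at 5/5/5 |
|---|---|---|---|
| IUGR minus healthy (1 SD) | 1/0.577 = 1.73 in size | 36.5% | 30.7% |
| diabetes minus healthy (1 SD) | 1/0.606 = 1.65 | 33.7% | 30.7% |
| IUGR minus diabetes (2 SD) | 2/0.606 = 3.30 in size | 86.6% | 82.7% |
| Omnibus F, for comparison | – | 75.9% | 70.2% |

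In a simulation of 200,000 studies under this pattern at 6/6/5, 57% of the significant F results came without a significant finding that diabetes exceeds healthy.

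**Step 5: precision.** The 95% half-width is t(0.975; 14) × √(1/na + 1/nb). It is 2.145 × 0.577 = 1.24 SD for IUGR minus healthy, and 2.145 × 0.606 = 1.30 SD for either difference involving diabetes.

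**The case against.** The strongest reply is that this is an exploratory pilot, that section 4.1 disclaims power, and that section 4.4 speaks of comparisons in the plural and waives multiplicity adjustment. That wording fits unadjusted pairwise tests after the ANOVA. A fitted one-way model also yields group means and a residual SD, so the cohort differences can be recovered. Much of this stands. The documents do not show that F is the only result anyone will look at. But no pairwise test is named, and the waiver may refer only to several outcomes, so which comparisons decide Hypothesis 1 is left open. Exploratory status excuses low power; it does not turn an undirected test into a test of a directed statement.

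Three stronger readings are tempting and should be resisted.

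- *The omnibus test is less powerful than the matching contrasts.* This is not true in general. Under −1/0/+1 at 5/5/5, F has 70.2% power against 30.7% for each contrast with healthy. Only IUGR minus diabetes does better, at 82.7%. F draws its power from the wide IUGR-diabetes gap, which answers a different question.
- *A (−1, 0, +1) contrast would test the predicted order.* Healthy gets weight zero, so the contrast is simply diabetes minus IUGR. At 5/5/5 it is significant in 82.7% of studies under −2/0/0, and equally under −1/+2/+1, where healthy is highest.
- *The plan will carry eta-squared or f forward.* Section 4.4 never says which effect size it means.

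**Conclusion.** The point holds as a mismatch between hypothesis and test. A significant F from the ANOVA in section 4.4 does not establish either part of Hypothesis 1, because it ignores sign and does not say which cohort differs. That conclusion is structural and needs no assumed effect size.

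The 83% illustration rests on normal data, a common SD, 5 completers per cohort and an assumed 2 SD deficit in IUGR alone. Under smaller assumed shifts at 6/6/5 the corresponding figures are 66% and 55%. It is not a finding about lost power, and the documents do not support one. The weight of the point is tempered by the pilot's exploratory, unpowered status, but the estimates it leaves unspecified are the ones the next study will need.

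**What to change.** Keep the three-group model and add to section 4.4 the comparisons that decide Hypothesis 1, each reported as an estimate with a 95% confidence interval and with sidedness stated:

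- IUGR minus healthy, and IUGR minus diabetes, for visceral, subcutaneous and brown fat. Part 1 is judged on both.
- Diabetes minus healthy, for visceral and subcutaneous fat. Part 2 is judged on this.

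Apply them to volume and PDFF, since Hypothesis 1 names both. State that these differences and the residual SD will feed the later power calculation. Do not add a (−1, 0, +1) contrast as a test of order.

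The cost is SAP wording only, with no extra mothers, scans or data. The downside is that the contrasts with healthy have about 34-37% power for a 1 SD difference at 6/6/5, with intervals of about ±1.2 to 1.3 SD. A non-significant difference must not be read as evidence of no difference. Their main use is estimation.
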